4. LIST OF ABBREVIATIONS AND DEFINITIONS OF TERMS

Abbreviation or Specialist Term	Explanation
15-HETE	15-LOX–derived 15-hydroxyeicosatetraenoic acid
ACC	Acetyl-CoA carboxylase
Adipo-IR	Adipose tissue insulin resistance
AE	Adverse event
ALT	Alanine aminotransferase
ANCOVA	Analysis of covariance
ANOVA	Analysis of variance
ApoB	Apolipoprotein B
APRI	AST to platelet ratio
AST	Aspartate aminotransferase
ATP III	Adult Treatment Panel III
BMI	Body mass index
CAP	Controlled attenuation parameter
CFDA	China Food and Drug Administration
CK-18	Cytokeratin-18
CMH	Cochran-Mantel-Haenszel
CoA	Coenzyme A
COVID-19	Coronavirus disease-2019
CRA	Clinical research associate
CTCAE	Common Terminology Criteria for Adverse Events
CYP3A4	Cytochrome P450 3A4
DILI	Drug-induced liver injury
DLT	Dose-limiting toxicity
DNL	De novo lipogenesis
ECG	Electrocardiogram
eCRF	Electronic case report form
EDC	Electronic data capture
ELF	Enhanced liver function
ELISA	Enzyme-linked immunosorbent assay
FASN	Fatty acid synthase
FIB-4	Fibrosis-4

Abbreviation or Specialist Term	Explanation
GCP	Good Clinical Practice
GGT	Gamma-glutamyl transpeptidase
GLP	Good Laboratory Practice
HbA1c	Glycated hemoglobin
HBsAg	Hepatitis B surface antigen
HCV	Hepatitis C virus
HDL-C	High-density lipoprotein cholesterol
HOMA2-IR	Homeostatic model assessment insulin resistance
Hs-CRP	High-sensitivity C-reactive protein
ICH	International Council for Harmonisation
IL	Interleukin
IL-6	Interleukin 6
INR	International normalized ratio
IRB	Institutional Review Board
IST	Investigator-sponsored trial
ITT	Intent-to-treat population
IUD	Intrauterine device
LDL-C	Low-density lipoprotein cholesterol
Lp(a)	Lipoprotein(a)
LTB4	5-LOX-derived leukotriene B4
LXA4	Lipoxin A4
MCP-1	Monocyte chemoattractant protein-1
mITT	Modified intent-to-treat population
MRE	Magnetic resonance elastography
MRI-PDFF	Proton density fat fraction by magnetic resonance imaging
MRS	Magnetic resonance spectroscopy
MTD	Maximum tolerated dose
NADPH	Nicotinamide adenine dinucleotide phosphate
NAFLD	Non-alcoholic fatty liver disease
NAS	NAFLD activity score
NASH	Non-alcoholic steatohepatitis
NCI	National Cancer Institute

Abbreviation or Specialist Term	Explanation
NEFA	Non-esterified fatty acid
NMR	Nuclear magnetic resonance
NOAEL	No observed adverse effect level
OAD	oral anti-diabetic
PCR	Polymerase chain reaction
PD	Pharmacodynamic
PGE2	prostaglandin E2
PK	Pharmacokinetic
PO	Orally
PPE	Palmar-plantar erythrodysesthesia
QD	Once daily
RNA	Ribonucleic acid
SAP	Statistical analysis plan
SARS-CoV-2	Severe acute respiratory syndrome coronavirus-2
SRC	Safety Review Committee
TEAE	Treatment-emergent adverse event
TG	Triglycerides
TNF α	Tumor necrosis factor-alpha
ULN	Upper limit of normal
US	United States
US FDA	United States Food and Drug Administration
VCTE	Vibration-controlled transient elastography
β -HCG	Beta-human chorionic gonadotropin

5. INTRODUCTION

Fatty acid synthase (FASN) is a key enzyme in the de novo lipogenesis (DNL) pathway and catalyzes the biosynthesis of palmitate from acetyl-coenzyme A (CoA) and malonyl-CoA substrates, which can then undergo further modifications into other fatty acids and complex lipids. Because FASN catalyzes the last step in the fatty acid biosynthetic pathway, it is believed to be a determinant of the maximal liver capacity to synthesize fatty acids by DNL ([Postic, 2008](#)).

Dysregulation of FASN activity is found in a number of different disease states including cancer ([Buckley, 2017](#)) and metabolic diseases.

Metabolic diseases spanning the continuum of metabolic syndrome, non-alcoholic fatty liver disease (NAFLD) and the more advanced disease of non-alcoholic steatohepatitis (NASH) can progress to significant liver diseases, including cirrhosis and hepatocellular carcinoma. In addition, NAFLD is associated with increased comorbidities, including cardiovascular diseases ([Widya et al. 2016](#); [Targher, Day, and Bonora 2010](#)) and type 2 diabetes ([Cusi 2016](#)). Obesity and the metabolic syndrome are two key risk factors for NAFLD, which are characterized as an imbalance in energy utilization and storage ([Grundy, 2005](#)). This imbalance may lead to dysregulated metabolic pathways and inflammatory responses that drive further changes leading to liver damage and comorbid conditions. Over the next 5 years, NASH will overtake hepatitis as the most prevalent liver disease in the United States (US).

Normal responses to feeding carbohydrate in meals include a transient increase in hepatic DNL, a FASN-dependent pathway, followed by a return to baseline levels upon fasting. In subjects with NAFLD, however, hepatic DNL is increased ([Donnelly et al. 2005](#); [Lambert et al. 2014](#)), and FASN gene expression has been shown to be elevated in liver biopsies from NAFLD patients ([Kohijimi, 2007](#); [Mitsuyoshi, 2009](#)), contributing to elevated liver stores of triglycerides (TG) and saturated fatty acid species, which in turn may contribute to liver inflammation ([Wei 2006](#)), tissue damage, and fibrosis.

There are currently no drugs licensed for the treatment of NASH. Inhibiting lipogenesis, with an FASN inhibitor for example, may be a viable clinical strategy to address NASH.

Pharmacological inhibition of FASN with TVB-3664, a chemical surrogate of TVB-2640, improved hepatic steatosis, inflammation and fibrosis in a diet-induced mouse model of NASH ([Duke 2017](#)). Moreover, studies in NASH subjects have shown that inhibition of DNL with acetyl-CoA carboxylase (ACC) inhibitor GS-0976 ([Stiede, 2017](#)) results in a significant reduction of intrahepatic fat and surrogate markers of fibrosis and cell death ([Loomba, 2017](#)). Also, pioglitazone use has been shown to improve advanced fibrosis in NASH ([Musso, 2017](#)), which may be associated with a reduction in DNL ([Beysen, 2008](#)). Further studies are needed, however, to evaluate the full spectrum of treatment effects elicited by these drugs and management of their side-effects.

Sagimet Biosciences (formerly 3-V Biosciences) has developed an oral, once-daily (QD) FASN inhibitor, TVB-2640. This drug has been evaluated in approximately 160 humans to date including patients with solid tumors and healthy adults, some of whom had characteristics of metabolic syndrome. The safety, pharmacokinetic (PK) and pharmacodynamic (PD) parameters of TVB-2640 have been measured. Preliminary results demonstrated that once-daily, oral administration of TVB-2640 for 10 days decreased hepatic DNL in a dose-dependent manner and improved other markers of metabolic dysfunction in otherwise healthy subjects with

characteristics of the metabolic syndrome (Study 2006432, Syed-Abdul, 2019). These observations form the basis for evaluating the TVB-2640 as a novel therapy for subjects with NASH.

5.1. TVB-2640

The clinical safety profile to date for TVB-2640 is based primarily on one completed uncontrolled open-label Phase 1 study in humans (Study 3V2640-CLIN-002) in 136 patients with solid tumors, 76 treated with monotherapy (at doses ranging from 60 mg/m² to a dose of 240 mg/m² (i.e., up to 600 mg) and 60 treated with TVB-2640 in combination with a taxane (paclitaxel or docetaxel).

Overall, TVB-2640 demonstrated a favorable tolerability profile. Most treatment-emergent adverse events (TEAEs) were Grade 1 or 2 in intensity, non-serious, and manageable.

As anticipated, based on nonclinical study findings, the principal toxicities associated with TVB-2640 as monotherapy were skin and ocular effects. With monotherapy, most skin events were Grade 1 or 2 in intensity, and all were non-serious.

The maximum tolerated dose (MTD) of TVB-2640 monotherapy in patients with solid tumors was determined to be 100 mg/m². Dose-limiting toxicities (DLTs) associated with TVB-2640 monotherapy were skin and ocular events, including corneal edema, keratitis, and palmar-plantar erythrodysesthesia (PPE) syndrome.

As monotherapy, the most common individual TEAEs were alopecia (61%), PPE syndrome (46%), fatigue (37%), decreased appetite (26%), and dry skin (22%).

When TVB-2640 was administered in combination with a taxane (paclitaxel or docetaxel), skin and ocular effects also were common. Most skin events were Grade 1 or 2 in intensity, and all but 1 skin event were non-serious.

As was the case with monotherapy, the MTD of TVB-2640 in combination with paclitaxel was determined to be 100 mg/m². DLTs associated with TVB-2640 in combination included PPE syndrome and uveitis. The most common TEAEs with TVB-2640 in combination with paclitaxel were fatigue (53%), alopecia (46%), PPE syndrome (46%), nausea (40%), and peripheral neuropathy (36%). Peripheral neuropathy is known to be associated with paclitaxel.

When TVB-2640 was administered in combination with paclitaxel, 6 episodes of serious pneumonitis were experienced by 5 patients, with all assessed by the Investigator as related to both TVB-2640 and paclitaxel. (No cases of pneumonitis were reported among monotherapy patients.) Given the occurrence of these events, respiratory events were identified as adverse events of special interest for patients receiving TVB-2640 in combination.

Overall, among patients with solid tumors treated with TVB-2640, no apparent trends were seen over time or across TVB-2640 dose groups with regard to change from baseline in clinical laboratory or vital sign parameters. Furthermore, based on review of electrocardiogram (ECG) and Holter monitoring data, TVB-2640 was shown to have no clinically relevant QTc prolonging effect.

A total of 12 subjects with features of the metabolic syndrome have been treated with TVB-2640 at flat doses of 50 to 150 mg QD orally (PO) for 10 days in an Investigator-sponsored trial (IST).

TVB-2640 was well tolerated in this subject population. All TEAEs were Grade 1 in intensity and non-serious and none led to study drug discontinuation. The only TEAEs reported for >1 subjects were alopecia and PPE syndrome (each 2 subjects). In this study, QD PO administration of TVB-2640 for 10 days was shown to decrease hepatic DNL in a dose-dependent manner and improved other markers of metabolic dysfunction in this population of otherwise healthy subjects with characteristics of the metabolic syndrome. These observations form the basis for evaluating the TVB-2640 as a novel therapy for subjects with NASH.

Refer to the Investigator's Brochure for more detailed information regarding TVB-2640.

6. OBJECTIVES AND PURPOSE

6.1. Primary Objectives

The primary objectives are:

- To determine the effect of QD TVB-2640 for 12 weeks versus placebo on the change in hepatic fat fraction by proton density fat fraction by magnetic resonance imaging (MRI-PDF) from baseline in subjects with NASH.
- To determine the safety of QD TVB-2640 versus placebo in subjects with NASH, including the effects on alanine aminotransferase (ALT) and aspartate aminotransferase (AST).

6.2. Secondary Objective

The secondary objective is:

- To determine the effect of QD TVB-2640 for 12 weeks versus placebo in subjects with NASH on:
 - Lipid and lipoprotein parameters, including low-density lipoprotein cholesterol (LDL-C), non-LDL-C, high-density lipoprotein cholesterol (HDL-C), non-HDL-C, total cholesterol, TG, apolipoprotein B (ApoB), and lipoprotein(a) (Lp[a]) particles.
 - NASH and fibrosis biomarkers including cytokeratin-18 (CK-18), fibrosis-4 (FIB-4), and enhanced liver function (ELF) or FIBROSpect 2 or ProC3 test.
 - Eicosanoid panel.

6.3. Exploratory Objectives

The exploratory objectives are:

- To determine the effect of QD TVB-2640 for 12 weeks versus placebo in subjects with NASH on clinical measures, including:
 - Liver fibrosis, as determined by vibration-controlled transient elastography (VCTE).
 - Metabolic parameters, including fasting glucose, insulin, homeostatic model assessment insulin resistance (HOMA2-IR), HbA1c, non-esterified fatty acid (NEFA), adipose tissue insulin resistance (adipo-IR), adiponectin, resistin, Interleukin 6 (IL-6), and gamma-glutamyl transpeptidase (GGT).
 - Anthropometric parameters, including weight, waist and hip circumference, waist-hip ratio, and blood pressure.
 - Lipidomic analyses for DNL.
- Explore the relationship of plasma drug exposure to changes in efficacy and safety biomarkers.

- Explore possible relationships between genomic markers of NASH and responses to treatment.

6.4. Endpoints

6.4.1. Efficacy Endpoints

The primary efficacy endpoint is:

- Percent change from baseline in liver fat at Week 12, as determined by MRI-PDFF.

The key secondary efficacy endpoint is:

- The percentage of subjects with at least a 30% reduction in liver fat at Week 12, as determined by MRI-PDFF.

Additional efficacy endpoints are:

- Percent change from baseline in liver fat at Week 16, as determined by MRI-PDFF.
- Percentage of subjects with at least a 30% reduction in liver fat at Week 16, as determined by MRI-PDFF.
- Change from baseline over the 12-week treatment period in:
 - Liver aminotransferases.
 - Lipid and lipoprotein parameters.
 - NASH and fibrosis markers.
 - Eicosanoids.

Exploratory efficacy endpoints are:

- Change from baseline over the 12-week treatment period in:
 - Liver fibrosis, as determined by VCTE.
 - Metabolic parameters.
 - Anthropometric parameters.
 - Lipidomic analyses for DNL.
- Proportion of subjects with <5% liver fat (normalized) at Week 12.

6.4.2. Safety Endpoints

Safety endpoints are:

- Proportion of subjects experiencing treatment-emergent adverse events (TEAEs), Grade 3 or 4 TEAEs, and serious adverse events (SAEs).
- Change from baseline in vital sign measurements, 12-lead electrocardiogram (ECG) findings, and clinical laboratory test results.
- Proportion of subjects experiencing treatment-emergent ophthalmologic abnormalities.

7. INVESTIGATIONAL PLAN

7.1. Overall Study Design

This is a multi-center, randomized, single-blind, placebo-controlled, dose-escalation study to evaluate the safety and efficacy of TVB-2640 in subjects with NASH. Male and female subjects aged ≥ 18 years with either biopsy-proven NASH within 2 years before randomization and MRI-PDF $\geq 8\%$ or, if prior liver biopsy was not performed or results are not available, magnetic resonance elastography (MRE) ≥ 2.5 kpa (Cohorts 1 and 2 only) and MRI-PDF $\geq 8\%$ during screening are planned to be enrolled. Approximately 117 unique subjects will be enrolled and randomized, with at least 90 subjects enrolled in the US and approximately 27 evaluable subjects enrolled in China (18 active and 9 placebo). In the US, subjects will be enrolled and randomized to achieve 90 evaluable subjects (30 active and 15 placebo in each of 2 dose cohorts). The 50 mg cohort will enroll and randomize approximately 27 additional subjects from China. The US-only 75 mg cohort will enroll approximately 10 active, evaluable subjects who previously received placebo in the 25 or 50 mg cohort. A subject is defined as evaluable if they receive study drug for at least 8 weeks and have a baseline and at least 1 post-baseline MRI-PDF assessment on or after Week 8.

Subjects will be screened for study eligibility within 60 days before randomization. Subjects must meet all of the inclusion criteria and none of the exclusion criteria to participate in the study. Note that subjects who initially fail to meet all entrance criteria based on screening assessments (i.e., screen failures) may be submitted for re-screening once (see [Section 8.5](#) for details).

Subjects who are determined to be eligible for the study, based on screening assessments, are to be randomized into the study within 24 hours before baseline (Day 1, the first day of study drug administration). Subjects who are randomized are considered to be enrolled in the study. Initially, 2 TVB-2640 dose levels are planned to be evaluated in a sequential fashion: 25 mg and, if study suspension criteria are not met at the 25 mg dose level (see [Section 7.2](#)), 50 mg. At each of the 2 initial dose levels, subjects will be randomly assigned to TVB-2640 or placebo at a 2:1 ratio, with randomization stratified by type 2 diabetes mellitus status. The 50 mg dose level will also be stratified by country:

- 25 mg dose level: TVB-2640 (Planned N=30) and Placebo (Planned N=15)
- 50 mg dose level: US: TVB-2640 (Planned N=30) and Placebo (Planned N=15); China: TVB-2640 (Planned N=18) and Placebo (Planned N=9); Total: TVB-2640 (Planned N=48) and Placebo (Planned N=24)

Subjects will receive TVB-2640 or placebo QD PO for 12 weeks, or until the time of the final on-treatment MRI-PDF if after Week 12, but for no longer than 16 weeks. During the 12-week Treatment period, subjects are to attend study center visits at Week 1, Days 1 and 2, and Weeks 2, 4, 8, and 12. After completion of the 12-week Treatment period, subjects are to attend a Follow-up visit at Week 16 for post-treatment safety and efficacy assessments.

All subjects must complete the 12-week treatment period at the 25 mg dose level, with review of all safety data and written approval by the Safety Review Committee (SRC) and reviewed by the

Food and Drug Administration (FDA) before enrollment and treatment of subjects at the 50 mg dose level may commence.

After completion of Cohorts 1 and 2, and again if no stopping criteria are met upon review by the Independent SRC, subjects assigned to placebo in either cohort are eligible to crossover to receive TVB-2640 75 mg in Open-label Cohort 3 (planned N=12 in order to obtain 10 evaluable subjects). Cohort 3 will be conducted at select sites only.

The Sponsor notes that the coronavirus disease-2019 (COVID-19) pandemic may impact the conduct of the 50 mg and 75 mg cohorts, with challenges potentially arising from quarantines and travel limitations affecting study subjects as well as clinic and imaging facility closures. Accordingly, safety assessments scheduled for the Week 12 and 16 visits, as identified in [Table 2](#), including sample collection for clinical laboratory tests, physical examinations, and documentation of adverse events (AEs), may be performed at an alternate study center or by home health care visit. Furthermore, if the subject is unable to attend the Week 12 visit at the study center, one MRI-PDFF may be performed at any time between Week 11 and 16. If this scan is performed after Week 12, the subject must continue to receive study drug until the final scan is performed; however, study drug is not to be continued for >16 weeks. The safety of subjects who continue dosing beyond 12 weeks will be assessed during this continued dosing period by planning for blood sample collection at an alternate site or home visit at Week 12 and blood sample collection and physical examination on the last day of dosing. A 4-week off treatment safety assessment is to occur after the last dose, regardless of whether a subject receives treatment for 12 or 16 weeks.

In Cohorts 1 and 2, study drug will be dispensed to subjects in a single-blinded fashion. All other study personnel, with the exception of personnel conducting/interpreting imaging studies (see [Section 11.1](#)) at each study center, will be unblinded to the subject's treatment assignment. In Cohort 3, study drug will be dispensed in an open-label fashion.

Efficacy variables include MRI-PDFF as well as measurement of liver aminotransferases, lipid parameters, and markers of NASH and liver fibrosis. The primary endpoint is percent change from baseline in liver fat from baseline at Week 12, as determined by MRI-PDFF. The percentage of subjects with at least a 30% reduction in the primary endpoint is a key secondary efficacy endpoint.

In Cohorts 1 and 2, subjects will undergo MRI-PDFF prior to the start of treatment (pre-dose), at the end of the initial 12-week Treatment Period (between 11 and 12 weeks after the start of treatment), and at Week 16. Due to the COVID-19 pandemic, if the subject is unable to attend the Week 12 visit, one MRI-PDFF may be performed at any time between Week 11 and 16. If this scan is performed after Week 12, the subject must continue to receive study drug until the final scan is performed. However, study drug is not to be continued for >16 weeks. In Cohort 3, MRI-PDFF will undergo MRI-PDFF prior to the start of treatment (pre-dose) and at the end of the initial 12 week Treatment Period (between 11 and 12 weeks after the start of treatment).

During the study, safety will be assessed by vital signs (oral temperature, pulse, respiratory rate, and seated blood pressure), 12-lead ECG, physical examination, including ophthalmologic examination, and clinical laboratory testing (hematology, chemistry, and urinalysis). Subjects will be evaluated for AEs and concomitant medication use throughout the study.

Blood samples will be collected at specified times for the assessment of PK.

An SRC will oversee the study to ensure subject safety and to advise if any dosing alterations are recommended. The SRC will review safety including liver-related events (i.e., clinically meaningful elevations in ALT, AST, and bilirubin), and other efficacy (lipid parameters) and safety data as needed.

7.2. Study Suspension Criteria

Treatment of ongoing subjects and enrollment of new subjects at a given dose level will be suspended in the event of any of the following:

- One subject experiences a Grade 5 TEAE (i.e., TEAE with a fatal outcome).
- Two subjects experience the same Grade 4 TEAE.
- Three subjects experience the same Grade 3 TEAE.

In such cases, the SRC will review unblinded data to determine the relationship of the TEAE(s) to TVB-2640 and make a determination whether enrollment and treatment of subjects may be resumed or is to be permanently discontinued.

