Lymphocyte subsets in peripheral blood mononuclear cells (Cohorts 1 and 2 only) ^{22,26}		X						X		
Sample for storage ^{22,27}		X						X	X	
Spot urine sample collection for:										
Exploratory PD biomarkers ²²		X						X	X	
Study Drug Administration										
Randomization		X ²⁸								
Study drug dispensation		X			X	X				
Study drug administration		QD PO from Day 1 through Week 12								
Study drug accountability				X	X	X	X	X		

Table footnotes appear on the following page.

- 1 Baseline evaluations are to be performed pre-dose, unless otherwise specified.
- 2 At the time of this amendment, subject participation in the 25 mg cohort is complete, with participation in the 50 mg cohort fully enrolled but with subject participation ongoing. The Sponsor notes that the COVID-19 pandemic may impact the conduct of the 50 and 75 mg cohorts, with challenges potentially arising from quarantines and travel limitations affecting study subjects as well as clinic and imaging facility closures. Accordingly, safety assessments scheduled for the Week 12 and 16 visits, including sample collection for clinical laboratory tests, physical examinations, and documentation of AEs, may be performed at an alternate study center or by home health care visit. Furthermore, if the subject is unable to attend the Week 12 visit at the study center, one MRI-PDFP may be performed at any time between Week 11 and 16. If this scan is performed after Week 12, the subject must continue to receive study drug until the final scan is performed; however, study drug is not to be continued for >16 weeks. The safety of subjects who continue dosing beyond 12 weeks will be assessed during this continued dosing period by planning for blood sample collection at an alternate site or home visit at Week 12 and blood sample collection and physical examination on the last day of dosing. A 4-week off treatment safety assessment is to occur after the last dose, regardless of whether a subject receives treatment for 12 or 16 weeks.
For subjects in Cohort 3, Week 16 assessments may serve as screening assessments if within the window before the Day 1 visit.

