12.2.3. Recording Adverse Events

Each subject must be carefully monitored for the development of any AEs. This information should be obtained in the form of non-leading questions (e.g., “How are you feeling?”) and from signs and symptoms detected during each examination, observations of study personnel, and spontaneous reports from subjects.

All AEs (serious and non-serious) spontaneously reported by the subject and/or in response to an open question from study personnel or revealed by observation, physical examination, or other diagnostic procedures will be documented in the subject’s source documents and recorded in the eCRF. Any clinically relevant (as determined by the Investigator) deterioration in laboratory assessments or other clinical findings is considered an AE and must be recorded in the subject’s source documents and in the eCRF.

Information about AEs will be collected from screening (i.e., after the ICF is signed) through 28 days after the last dose of study drug. The AE term should be reported in standard medical terminology when possible. Also when possible, signs and symptoms indicating a common underlying pathology should be noted as one comprehensive event. For each AE, the investigator will evaluate and report the onset date, resolution date, intensity, causality, action taken, serious outcome (if applicable), and whether or not it caused the subject to discontinue the study.

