3.4. Safety Review Committee

An SRC will oversee the study to ensure subject safety and to advise if any dosing alterations are recommended. The SRC will review safety including liver-related events (i.e., clinically

Sponsor: Sagimet Biosciences
Protocol Number: 3V2640-CLIN-005
Version and Date: Final Version 1, 02June2020

meaningful elevations in ALT, AST, and bilirubin), and other efficacy (lipid parameters) and safety data as needed.

If study suspension criteria are met at any time (see Protocol Section 7.2), the SRC will review the relevant study data and make a determination whether enrollment and treatment of subjects may continue or be permanently terminated. In addition, the SRC will review all safety data from the 25 mg dose level after all subjects at that dose level complete the 12-week treatment period. Enrollment and treatment of subjects at the 50 mg dose level may commence only with the written approval of the SRC and with FDA review. The SRC may also review data from the 50 mg cohort, if performed, upon request (see below).

Additional details on the SRC can be found in the SRC Plan. The SRC Plan includes details on membership, purpose, organization, data requirements, logistics, and reporting requirements.

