8.5.1. Adverse Events

An AE is any untoward medical occurrence in a patient or clinical investigation subject administered a pharmaceutical product, and which does not necessarily have to have a causal relationship with this treatment. An AE can therefore be any unfavorable and unintended sign (including abnormal laboratory findings), symptom, or disease temporally associated with the use of an investigational product, whether or not related to the investigational product.

An unexpected AE is any event for which the nature or severity is not consistent with the information in the current Investigator's Brochure.

Any abnormal clinical or laboratory finding considered by the Investigator to be clinically significant is to be recorded in the eCRF as part of the subject's medical history if occurring prior to the start of study drug administration and as an AE if occurring after the start of study drug administration at baseline, where the finding represents a change from baseline.

A treatment emergent AE (TEAE) is defined as any AE occurring after the first dose of study treatment. All summaries of AEs will be based on TEAEs. All AEs recorded on the eCRF, whether treatment emergent or not, will be presented in the data listing. Non-TEAEs will be flagged in the listings.

Adverse Events will be coded using MedDRA version 22.0 Mar 2019 for reporting by SOC and PT. Summaries of TEAEs by SOC and PT will be presented in descending order of overall incidence. TEAEs will also be summarized by maximum intensity as classified according to the National Cancer Institute (NCI) Common Terminology Criteria for Adverse Events (CTCAE), Version 5.0. If the AE is not included in the NCI CTCAE, then the Investigator is to determine the severity of the AE according to the criteria provided in the study protocol. The causal relationship of each AE to study drug will be determined by the Investigator according to best medical judgment as definitely related, probably related, possibly related, unlikely related, or unrelated. If the relationship between the AE and study drug is determined to be "possible", "probable", or "definite", the event will be considered to be treatment-related for the safety analyses.

Any missing severity assessments will be assumed to be Grade 3 (severe) and missing relationship assessments will be assumed to be related. All AE summaries will be produced using the safety population and displayed by treatment group and overall.

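### Read literally, Section 7.2 suspends dosing for three Grade 3 cases of the same TEAE but not for two Grade 3 cases plus one Grade 4 case

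*Protocol*

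**What the plan says.** Protocol Section 7.2 lists three alternative triggers for suspending both treatment and enrollment at a dose level: one Grade 5 TEAE; "Two subjects experience the same Grade 4 TEAE"; "Three subjects experience the same Grade 3 TEAE". After a suspension the SRC reviews unblinded data and decides whether to resume or stop for good. Section 8.7 ties the SRC's continue-or-terminate decision to these criteria being met.

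The criteria also bear on escalation. Protocol Section 7.1 allows 50 mg only "if study suspension criteria are not met at the 25 mg dose level", and 75 mg after Cohorts 1 and 2 and "again if no stopping criteria are met upon review by the Independent SRC".

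On grading, Protocol Section 12.2.2.1 defines Grades 3 and 4 as separate categories. Section 12.2.3 says: "For each AE, the investigator will evaluate and report the onset date, resolution date, intensity, causality, action taken". In the SAP, Section 8.5.1 says "TEAEs will also be summarized by maximum intensity" and uses cumulative wording (Grade 3 or higher) for some AE tables. On how the committee works, SAP Section 3.4 says "Additional details on the SRC can be found in the SRC Plan"; that plan is not among the documents reviewed.

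**The concern.** A suspension rule should not become less likely to fire when one case in a set gets worse. Take three subjects at one dose level with the same Grade 3 TEAE: dosing stops. Make one of those cases life-threatening and, on the literal wording, the Grade 3 count falls to two, the Grade 4 count is one, and nothing fires.

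Section 7.2 is the protocol's only automatic dose-level stop. A missed trigger therefore also misses the SRC decision that Section 8.7 attaches to it, and leaves the escalation condition formally unviolated.

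**Working it through.** **The plan's own figure.** Section 7.2 gives thresholds and no operating characteristic. The only safety probability in the plan (Protocol Section 13.1, SAP Section 3.3) is that of seeing at least one AE among 30 subjects at a 10% rate: 1 − 0.9^30 = 0.958, which agrees with the stated minimum of 95%.

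**Logic.** Let n3 and n4 be the numbers of subjects at one dose level with the same TEAE at Grade 3 and at Grade 4, each subject counted at one grade. Grade 5 can be ignored, since one case suffices.

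- As written: suspend if n3 ≥ 3 or n4 ≥ 2.
- Cumulative: suspend if n3 + n4 ≥ 3 or n4 ≥ 2.

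| n3 | n4 | As written | Cumulative |
|---|---|---|---|
| 3 | 0 | suspend | suspend |
| 2 | 1 | continue | suspend |
| 1 | 2 | suspend | suspend |
| 0 | 2 | suspend | suspend |
| 1 | 1 | continue | continue |
| 2 | 0 | continue | continue |

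The rules can differ only where n3 ≤ 2, n4 ≤ 1 and n3 + n4 ≥ 3, which leaves (2, 1) alone.

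**Size.** The planned numbers come from Protocol Section 7.1: 12 subjects at 75 mg and 48 active at 50 mg. Everything else is assumed: p is the chance that a subject has a Grade 3 or 4 case of one event type, q is the share of those at Grade 4, and subjects are independent. The difference between the rules is the probability of exactly (2, 1):

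gap = 3 · C(n,3) · p³ · q(1−q)² · (1−p)^(n−3)

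Example, n = 48, p = 0.05, q = 0.2: 3 × 17,296 × 0.000125 × 0.128 × 0.95^45 (0.0994) = 0.083.

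With q = 0.2:

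| n | p | As written | Cumulative | Gap (points) |
|---|---|---|---|---|
| 12 | 2% | 0.2% | 0.2% | 0.06 |
| 12 | 5% | 1.7% | 2.4% | 0.7 |
| 12 | 10% | 8.7% | 12.0% | 3.3 |
| 48 | 2% | 5.7% | 7.8% | 2.1 |
| 48 | 5% | 36.1% | 44.4% | 8.3 |

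**Sensitivity to q.** The gap depends on q through q(1−q)²: 0.045 at q = 0.05, 0.128 at 0.2 and 0.148 at 1/3, where it peaks. At n = 48 and p = 5% the gap is 2.9, 8.3 and 9.6 points respectively.

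**Sensitivity to counting.** If a fraction f of Grade 4 cases is also counted at Grade 3, the gap is multiplied by (1 − f), and at f = 1 it is zero.

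These are whole-cohort figures for one event type. More event types would change them, so none is a bound on the rule as a whole.

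**The case against.** The strongest reply is that the literal reading is not forced. A subject who reaches Grade 4 may be regarded as having passed Grade 3, and no text rules that out. Section 12.2.3 lists intensity among the items reported for each AE but does not say it is recorded only once. A subject with separate Grade 3 and Grade 4 records would satisfy both lines. The maximum-intensity and Grade 3 or higher wording in SAP Section 8.5.1 governs tables, not suspension. The SRC Plan may already pool grades. All of this stands. It makes the gap conditional on a counting convention that the documents leave unstated; it does not supply the convention.

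The second reply is that subjects are watched in other ways. The SRC has standing oversight and may advise on dosing (Sections 7.1 and 8.7). It reviews before 75 mg and may look at 50 mg data on request (SAP Section 3.4), and it carried out an extra safety analysis before extended dosing (SAP Section 3.5). Study personnel other than imaging staff are unblinded (Section 9.9), so such a cluster on active drug would be visible to them. The sponsor may terminate (Section 7.3), and Section 8.6 and Appendix A stop individual subjects for skin, eye, respiratory and liver toxicity. These safeguards are real and reduce the consequence. They are discretionary or act on one subject, so they do not replace an automatic dose-level stop.

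A reader might infer that subjects were left unprotected, or that the SRC in fact ignored Grade 4 cases when counting Grade 3. The documents support neither: the safeguards above exist, and nothing shows how the SRC counts.

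**Conclusion.** The point holds as a wording defect in a safety rule. On the literal text, one combination, two Grade 3 cases plus one Grade 4 case of the same TEAE, is ranked below a milder set that suspends dosing. The conclusion rests on each subject being counted at one grade only.

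The size cannot be established from the documents. They give no Grade 3 or 4 rates for this population, and the 12 subjects with metabolic-syndrome features had Grade 1 TEAEs only (Protocol Section 5.1). The illustrative gaps, from about 0.1 to 9.6 points over the cases above, depend on assumed event rates and an assumed Grade 4 share. They should not be read as estimates or as upper limits.

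Practical reach is small. Footnote 2 to the schedule of events records 25 mg as complete and "participation in the 50 mg cohort fully enrolled but with subject participation ongoing". At that version only the remaining 50 mg dosing and the planned 12 subjects at 75 mg were exposed to the wording. The SAP addendum of March 2022 already refers to data from thirteen Cohort 3 subjects, so the value by then lies mainly in clarifying the rule and carrying it forward. This is a change to consider, not a flaw that undermines the trial.

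**What to change.** In Section 7.2, insert the words *or higher* after the grade in the third line, and add that each subject counts once per event at worst grade. Put the same counting rule in the SRC Plan if it is not already there. Leave the Grade 4 line alone, since a single Grade 5 case already suspends. Keep the thresholds, the Grade 5 line and the SRC's power to resume.

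The cost is a protocol amendment with IRB re-approval (Section 14.2), and somewhat more frequent pauses pending SRC review. Under the assumptions above, the increase at 75 mg is about 0.1 to 3.3 points for one event type. For a full 50 mg cohort it is about 2 to 8 points, and less for the part of that cohort's dosing still to come. If the SRC already counts a Grade 4 case at Grade 3, the edit records existing practice and adds no pauses.
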